2.4 Sample Size Determination

Sub-Study 1 (Phase 2b):

For Sub-Study 1 (Phase 2b portion of the study), approximately 240 subjects in the Bio-IR population will be equally randomized using a 1:1:1:1 ratio to three risankizumab treatment groups (600 mg, 1200 mg and 1800 mg IV Q4W) and the placebo group. The sample size for this study is based on the expected proportion of subjects who achieve clinical remission per Adapted Mayo Score at Week 12. Assuming clinical remission rate of 7% in the placebo arm and maximum of 25% in at least one of the risankizumab treatment groups at Week 12, a sample size of 60 subjects per treatment group is sufficient to test for the presence of a dose response signal, to select the best dose response model for the observed data out of a pre-specified set of candidate models, and to estimate target doses of interest (e.g., MED) via modeling using MCP-Mod (Multiple comparison procedure and modeling) approach.^{1,2} The assumptions for the rates of clinical remission were estimated based on the meta-analysis of Phase 3 induction studies of the marketed drugs for patient population who have had intolerance or inadequate response to prior biologic therapy. This approach provides an average power of approximately 87% to detect a dose effect at 5% level of significance (one-sided) with the linear, E_{max} ($ED_{50} = 600$ per dosing visit), exponential ($\delta = 600$ per dosing visit), logistic ($ED_{50} = 600$ per dosing visit and $\delta = 160$) and $sigE_{max}$ ($ED_{50} = 600$ per dosing visit and $h = 3$) models pre-specified as likely candidates to characterize the dose response for risankizumab for the primary endpoint of clinical remission at Week 12 per Adapted Mayo Score.

A minimum of 240 subjects will be enrolled into Study M16-067 Sub-Study 1 for dose selection analysis. The additional subjects enrolled during the dose selection analysis period will not be part of the dose selection analysis, but will be evaluated separately as exploratory in the final CSR.

3.0 Endpoints

Endpoint definitions (Sub-Study 1):

- **Clinical Remission per Adapted Mayo:** stool frequency subscore (SFS) ≤ 1 , and not greater than baseline, rectal bleeding subscore (RBS) = 0, and endoscopic subscore ≤ 1
- **Clinical Response per Adapted Mayo:** decrease from Baseline ≥ 2 points and $\geq 30\%$, PLUS a decrease in RBS ≥ 1 or an absolute RBS ≤ 1
- **Clinical Response per Partial Adapted Mayo (without endoscopy):** decrease from Baseline ≥ 1 points and $\geq 30\%$, PLUS a decrease in RBS ≥ 1 or an absolute RBS ≤ 1
- **Clinical Remission per Full Mayo:** Full Mayo score ≤ 2 with no subscore > 1
- **Endoscopic Improvement:** endoscopy subscore of 0 or 1
- **Endoscopic Remission:** endoscopic subscore = 0
- **Histologic Remission:** Geboes score < 2.0
- **Mucosal Healing:** endoscopic and histologic remission

Note: Evidence of friability during endoscopy in subjects with otherwise "mild" endoscopic activity will confer an endoscopic subscore of 2.

3.1 Primary Endpoint(s)

The primary endpoint for Phase 2b induction (Sub-Study 1) is the proportion of subjects who achieve clinical remission per Adapted Mayo score at Week 12.

3.2 Secondary Endpoint(s)

The secondary endpoints for Sub-Study 1 are:

Ranked Secondary Endpoints:

1. The achievement of endoscopic improvement at Week 12
2. The achievement of clinical remission per Full Mayo score at Week 12 in subjects with a Full Mayo score of 6 to 12 at Baseline
3. The achievement of clinical response per Adapted Mayo score at Week 12
4. The achievement of clinical response per Partial Adapted Mayo score at Week 4
5. The achievement of endoscopic remission at Week 12
6. Occurrence of hospitalizations through Week 12
7. The achievement of mucosal healing at Week 12
8. Change from Baseline in UC-Symptom Questionnaire (UC-SQ) at Week 12
9. Change from Baseline in Inflammatory Bowel Disease Questionnaire (IBDQ) at Week 12
10. Change from Baseline in Short Form-36 at Week 12
11. Change from Baseline in Functional Assessment of Chronic Illness Therapy-Fatigue (FACIT-F) at Week 12
12. UC-related surgeries through Week 12

Non-Ranked Secondary Efficacy Endpoints:

- The achievement of SFS = 0, RBS = 0, and endoscopic subscore = 0 at Week 12
- The achievement of SFS \leq 1 over time
- The achievement of RBS = 0 over time
- Change from Baseline in Partial Adapted Mayo score over time
- Change from Baseline in Full Mayo score at Week 12
- Change from Baseline in SFS over time
- Change from Baseline in RBS over time
- Change from Baseline in hs-CRP over time

- Change from Baseline in FCP over time
- Change from Baseline in Ulcerative Colitis Endoscopic Index of Severity (UCEIS) at Week 12
- The achievement of histologic remission at Week 12
- Change from Baseline in European Quality of Life 5 Dimensions (EQ-5D-5L) over time
- Change in Work Productivity and Impairment Questionnaire – UC (WPAI-UC) over time
- Time to clinical response per partial adapted Mayo score
- Change from baseline in Patient Global Impression of Severity (PGIS) over time
- Patient Global Impression of Change (PGIC) over time
- The achievement of clinical remission per Adapted Mayo over time
- The achievement of endoscopic improvement over time
- The achievement of endoscopic remission over time
- The achievement of no bowel urgency at Week 12
- The achievement of no abdominal pain at Week 12
- Achieving response in IBDQ bowel symptom domain (increase of IBDQ bowel symptom domain score ≥ 6 from baseline) at Week 12
- Change from Baseline in subject-reported stool frequency (absolute values)
- Change from Baseline in percentage of colonic segments with an endoscopic subscore ≤ 1 (local read)

3.3 Other Efficacy Endpoints

The primary and/or secondary efficacy endpoints are listed in Section 3.1 and/or Section 3.2, respectively. All the efficacy endpoints listed in Section 3.1 and Section 3.2 during Induction Period 2 are exploratory endpoints.

3.4 Safety Endpoint(s)

Adverse events, vital signs, physical examination results, and clinical laboratory data will be assessed throughout the study.

4.0 Analysis Populations

The following population sets will be used for the analyses.

Intent-to-Treat Analysis Set

Sub-Study 1 – Induction Period 1:

The Intent-to-Treat (ITT) Analysis Set for Induction Period 1 in Sub-Study 1 includes all randomized subjects who received at least one dose of study drug during Sub-Study 1 (denoted as ITT1A) at the time of dose-selection analysis. The set of all the additional subjects who received at least one dose of risankizumab 1800 mg IV treatment group after 240 subjects were randomized during the dose-selection period is denoted as ITT1B. The ITT for Induction Period 1 in Sub-Study 1 will be denoted ITT1 and will be the combination of ITT1A and ITT1B.

Sub-Study 1 Induction Period 2:

Subjects who received at least one dose of risankizumab during Induction Period 2 in Sub-Study 1 (denoted as ITT1_P2) will be analyzed separately for exploratory purposes.

Safety Analysis Set

For the safety analysis set in each sub-study, subjects will be analyzed in a treatment group based on the treatment actually received, not randomized. The safety analysis in each sub-study will be based on the corresponding safety analysis set.

Sub-Study 1 – Induction Period 1

The Safety Analysis Set for Induction Period 1 in Sub-Study 1 includes all subjects who received at least one dose of study drug during Induction Period 1 in Sub-Study 1 (denoted as SAS1A) at the time of dose-selection analysis. The set of all the additional subjects who received at least one dose of risankizumab 1800 mg IV treatment group after 240 subjects were randomized during the dose-selection period is denoted as SAS1B. The Safety Analysis Set for Induction Period 1 in Sub-Study 1 in Period 1 will be denoted SAS1 and will be the combination of SAS1A and SAS1B.

Sub-Study 1 Induction Period 2:

Subjects who received at least one dose of risankizumab during the Induction Period 2 after Week 12 in Sub-Study 1 (denoted as SAS1_P2) will be analyzed separately for exploratory purposes.

5.0 Subject Disposition

The number of subjects will be tabulated by country, investigator site and overall for the following sets: Induction Period 1 ITT1A, ITT1B and Induction Period 2 ITT1_P2 populations, Safety populations, subjects who completed study by period, and subjects who prematurely discontinued for study drug or study by period, for each treatment group and overall, as appropriate.

In addition, the number and percentage of subjects who discontinued study drug or study will be summarized by reason for each treatment group and overall. All reasons and primary reasons for discontinuation of study drug will be summarized as recorded on the eCRF by the following categories:

- Adverse event (AE)
- Lost to follow-up
- Withdraw consent
- Lack of efficacy

- COVID-19 infection
- COVID-19 logistical restrictions
- Other

Subjects may have more than one reason for discontinuing study drug, but they will be counted once for the total number of discontinuations. Subjects have only one primary reason for discontinuing study drug or discontinuing from the study.

6.0 Study Drug Duration and Compliance

Induction Period:

For the safety populations SAS1A and SAS1B, the duration of exposure to study drug will be summarized for each treatment group in the induction Period 1.

- Duration of exposure in the induction Period 1:
 - If the subjects went to Study M16-066 after the induction Period 1:
 - Duration of exposure = min (the first study drug dose date in Study M16-066 – the first study drug dose date in induction Period 1, the last study drug dose date in the induction period – the first study drug dose date in the induction period + 28 days),
 - If the subject went to the induction Period 2 after induction Period 1:
 - Duration of exposure = min (the first study drug dose date in the induction Period 2 – the first study drug dose date in induction Period 1, the last study drug dose date in induction Period 1 – the first study drug dose date in induction Period 1 + 28 days),
 - Otherwise:
 - Duration of exposure = the last study drug dose date in induction Period 1 – the first study drug dose date in induction Period 1 + 28 days,

Where study drug dose date refers to recorded dates of injections of study drug.

For each treatment group and total in the induction period, the duration of exposure will be summarized by the number of subjects treated, as well as the mean, standard deviation, median, minimum and maximum values. In addition, the number and percentage of subjects exposed to study drug will be summarized for the following exclusive duration intervals:

- 1 – 28 days
- 29 – 56 days
- 57 – 84 days
- 85 – 112 days
- > 112 days

Induction Period 2:

For the safety population SAS1_P2, the duration of exposure to study drug will be summarized for each treatment group in induction Period 2.

- Duration of exposure in induction Period 2:
 - If the subjects went to Study M16-066 after induction Period 2:
 - Duration of exposure = min (the first study drug dose date in Study M16-066 – the first study drug dose date in induction Period 2, the last study drug dose date in induction Period 2 – the first study drug dose date in induction Period 2 + 28 days),
 - Otherwise:
 - Duration of exposure = the last study drug dose date in induction Period 2 – the first study drug dose date in induction Period 2 + 28 days,

Where study drug dose date refers to recorded dates of injections of study drug.

For each treatment group and total in induction Period 2, the duration of exposure will be summarized by the number of subjects treated, as well as the mean, standard deviation,

median, minimum and maximum values. In addition, the number and percentage of subjects exposed to study drug will be summarized for the following exclusive duration intervals:

- 1 – 28 days
- 29 – 56 days
- 57 – 84 days
- 85 – 112 days
- > 112 days

Treatment compliance is calculated as follows:

$$TC = \frac{\text{Total number of injections and/or infusions received}}{\text{Total number of injections and/or infusions planned}} \times 100\%$$

Number of subjects receiving study drug and dose will be summarized for both periods in Sub-Study 1 and 2 based on safety analysis set using descriptive statistics. Subjects with missing data for the number of injections returned will be excluded from the summary.

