Subjects taking oral corticosteroids at Baseline must continue their concomitant treatment at the Baseline dose for the duration of Induction Period 1. Initiation and/or increasing doses of systemic and/or UC-related corticosteroids after Baseline is prohibited. Decreasing doses of oral corticosteroids is prohibited during Induction Period 1, except in the event of moderate-to-severe treatment related toxicities in the opinion of the investigator.

Methodology (Continued):

Subjects who enter Induction Period 2 will be allowed to taper their oral corticosteroids at the discretion of the Investigator. While stopping the taper is permitted, increasing doses above the Baseline dose is prohibited.

Dose Selection:

Sub-Study 2 (Phase 3 induction study) will evaluate IV risankizumab 1200 mg during induction. The selection of doses was informed by the analysis of safety and efficacy data, as well as the dose-response and exposure-response relationships of efficacy from Sub-Study 1 (Phase 2b dose finding study).

Induction Period 2 will evaluate IV (1800 mg [Sub-Study 1] or 1200 mg [Sub-Study 2] Q4W) or SC (180 mg or 360 mg Q8W; maintenance dosing regimen) risankizumab. The purpose of Induction Period 2 is to evaluate the efficacy and safety of re-induction of risankizumab versus starting maintenance regimen on clinical response status. Data from the Phase 2 study in subjects with CD suggested that re-induction with 600 mg IV increased both clinical response and clinical remission in subjects with inadequate response at Week 12. The selection of the SC doses is based on safety and efficacy data, as well as the exposure-response relationship, of the maintenance period during the Phase 2 study in subjects with CD that evaluated 180 mg SC risankizumab for maintenance. A higher dose of 360 mg Q8W is proposed to provide exposures reasonably separated with 180 mg Q8w dose to characterize the exposure-response relationship during maintenance phase with a potential of 360 mg Q8w dose to maintain higher response compared to 180 mg Q8w dose.

Data Monitoring Committee (DMC):

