6.0 Study Drug Duration and Compliance

6.1 Study Drug Duration

Induction Period 1

For the safety population SA2, duration of exposure to study drug will be summarized for each treatment group in Induction Period 1.

Duration of exposure in Induction Period 1:

- If the subjects enrolled into Study M16-066 after the Induction Period 1:
 - Duration of exposure = min (the first study drug dose date in Study M16-066 – the first study drug dose date in Induction Period 1, the last study drug dose date in the Induction Period 1 – the first study drug dose date in the Induction Period 1 + 28 days),
- If the subject enrolled into Induction Period 2 after Induction Period 1:
 - Duration of exposure = min (the first study drug dose date in the Induction Period 2 – the first study drug dose date in Induction Period 1, the last study drug dose date in Induction Period 1 – the first study drug dose date in Induction Period 1 + 28 days),
- Otherwise:
 - Duration of exposure = the last study drug dose date in Induction Period 1 – the first study drug dose date in Induction Period 1 + 28 days.

For each treatment group and total in Induction Period 1, the duration of exposure will be summarized by the number of subjects treated, as well as the mean, standard deviation, median, minimum and maximum values. In addition, the number and percentage of subjects exposed to study drug will be summarized for the following exclusive duration intervals:

- 1 – 28 days
- 29 – 56 days
- 57 – 84 days

- 85 – 112 days
- > 112 days

Induction Period 2

For the safety population SA2_P2, the duration of exposure to study drug will be summarized for each treatment group in Induction Period 2.

Duration of exposure in Induction Period 2:

- If the subjects enrolled into Study M16-066 after Induction Period 2:
 - Duration of exposure = min (the first study drug dose date in Study M16-066 – the first study drug dose date in Induction Period 2, the last study drug dose date in Induction Period 2 – the first study drug dose date in Induction Period 2 + 28 days [for IV dose] or 56 days [for SC dose]),
- Otherwise:
 - Duration of exposure = the last study drug dose date in Induction Period 2 – the first study drug dose date in Induction Period 2 + 28 days [for IV dose] or 56 days [for SC dose].

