2.3 Treatment Assignment and Blinding

Sub-Study 1 (Phase 2b Induction):

Induction Period 1:

Subjects (n = 240) who meet all of the inclusion criteria and none of the exclusion criteria will be randomized into the study in a 1:1:1:1 ratio to one of the following treatment groups:

- Group 1: Risankizumab 1800 mg IV Weeks 0, 4, 8 (n = 60)
- Group 2: Risankizumab 1200 mg IV Weeks 0, 4, 8 (n = 60)
- Group 3: Risankizumab 600 mg IV Weeks 0, 4, 8 (n = 60)

- Group 4: Placebo IV Weeks 0, 4, 8 (n = 60)

The randomization at baseline will be stratified by baseline steroid use (yes vs no) and baseline Adapted Mayo score (≤ 7 vs > 7). Endoscopy and evaluation of clinical response and remission will occur at Week 12.

Induction Period 2:

At Week 12, subjects who do not achieve clinical response will be randomized by Interactive Response Technologies (IRT) to Induction Period 2, a double-blind, double-dummy 12-week treatment period to evaluate reinduction with risankizumab versus starting maintenance dosing on clinical response status.

Subjects who received IV risankizumab induction will be randomized 1:1:1 to:

- Group 1: 1800 mg IV risankizumab Weeks 12, 16, 20
- Group 2: 360 mg SC risankizumab Weeks 12, 20
- Group 3: 180 mg SC risankizumab Weeks 12, 20

Subjects who received IV placebo induction treatment will receive:

- Group 4: 1800 mg IV risankizumab Weeks 12, 16, 20

Subjects randomized in Groups 1 and 4 will receive placebo SC and subjects randomized in Groups 2 and 3 will receive placebo IV, in order to keep the blind. The IV risankizumab dose or matching IV placebo will be given at Weeks 12, 16, and 20. The SC risankizumab dose or matching SC placebo will be given at Weeks 12, and 20.

Dose Selection Analysis:

During this analysis, Sub-Study 1 will continue to enroll additional subjects in the 1800 mg dosing group, on an open-label basis, to avoid interrupting the study activities

during the analysis period and to generate a sufficient number of subjects with clinical response to be enrolled into the maintenance Study M16-066.

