9.2.4 Treatment-Emergent Adverse Events per Patient-Years of Exposure

Exposure-adjusted AEs per 100 patient-years will be provided, where AEs per 100 patient-years of exposure are defined as the number of AEs divided by the total exposure in 100 patient-years.

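### Sub-Study 1 credits 28 days after the last Period 2 dose in every arm, where the Sub-Study 2 SAP credits 56 after SC dosing, so summarised SC exposure is up to 28 days shorter for subjects who do not enter M16-066

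*SAP*

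**What the plan says.** **Sub-Study 1 SAP, Section 6.0.** Period 2 duration has two branches. One applies "If the subjects went to Study M16-066 after induction Period 2" and takes the smaller of the time to the first M16-066 dose and last minus first dose plus 28 days. The other covers everyone else and has no cap. Both end in "the first study drug dose date in induction Period 2 + 28 days", with no split by route. A note adds: "Where study drug dose date refers to recorded dates of injections of study drug".

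**Sub-Study 2 SAP, Section 6.1.** The structure is the same, but the tail is "28 days [for IV dose] or 56 days [for SC dose"]. The all-risankizumab summary in that section keeps the split and counts from risankizumab dose dates.

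**Regimen.** Sub-Study 1 SAP, Section 2.3, lists "Group 2: 360 mg SC risankizumab Weeks 12, 20", with the 180 mg arm on the same weeks. The protocol synopsis gives the interval as "SC (180 mg or 360 mg Q8W; maintenance dosing regimen"). Period 2 is double-dummy: "subjects randomized in Groups 2 and 3 will receive placebo IV, in order to keep the blind", with infusions at Weeks 12, 16 and 20.

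**Adverse event rates.** Sub-Study 1 SAP, Section 9.2.4: "AEs per 100 patient-years of exposure are defined as the number of AEs divided by the total exposure in 100 patient-years". It does not refer to Section 6.0. Sub-Study 2 SAP, Section 10.2, uses last minus first dose plus 140 days for all routes. In Sub-Study 1 SAP, Section 9.2.1, the treatment-emergent window runs 140 days past the last dose, or to the first M16-066 dose.

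**The concern.** The two SAPs give the same SC regimen different lengths of exposure. The 28-day tail equals one IV dosing interval but only half an SC interval. Section 6.0 calls for means, medians and counts in 28-day bands by arm, so the choice shows directly in the Period 2 exposure table, and the SC arms of the two sub-studies cannot be read side by side.

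The affected group is real: Protocol Section 5.1 says that subjects without response at Week 24 were discontinued and did not roll over, so their duration has no cap. If the same duration were also used as the denominator in Section 9.2.4, adverse event rates would move too.

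**Working it through.** The documents state no exposure total to reproduce, so both rules are applied to the planned schedule.

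**Inputs.** Day 0 is Week 12. SC doses fall on days 0 and 56, and IV doses on days 0, 28 and 56 (Sub-Study 1 SAP, Section 2.3). Week 24 is day 84. Day 91 is Week 24 plus the 7-day visit window in Protocol Appendix C.

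**Formula.** Duration = (last dose − first dose) + tail, capped at the first M16-066 dose for those who enter.

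| SC subject in Period 2 | Sub-Study 1 rule | Sub-Study 2 rule | Difference |
|---|---|---|---|
| Both doses, not entering M16-066 | 56 + 28 = 84 | 56 + 56 = 112 | 28 |
| One SC dose, not entering, dummy infusions not counted | 0 + 28 = 28 | 0 + 56 = 56 | 28 |
| Both doses, entering on day 84 | min(84, 84) = 84 | min(84, 112) = 84 | 0 |
| Both doses, entering on day 91 | min(91, 84) = 84 | min(91, 112) = 91 | 7 |

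The first row moves from the 57–84 day band to 85–112, and the second from 1–28 to 29–56. An IV subject with all three doses who does not enter has 56 + 28 = 84 days under either SAP.

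**Arm mean.** The share of SC completers entering M16-066 is not given. Assume a share q enters on day 84. The Sub-Study 1 mean is 84 days; the Sub-Study 2 mean is 84q + 112(1 − q):

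- q = 30%: 25.2 + 78.4 = 103.6 days
- q = 50%: 42 + 56 = 98.0 days
- q = 70%: 58.8 + 33.6 = 92.4 days
- q = 100%: 84 days, no difference

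**Dose date.** An SC subject who stops after the Week 16 dummy infusion has 28 days under the Sub-Study 1 rule if only the SC dose counts, and 28 + 28 = 56 if the infusion counts. The injection note does not settle this. Section 6.0 attaches the same note to Period 1, where all study drug is infused, so it cannot be meant literally.

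**Adverse event denominator.** For a completer who does not enter M16-066, the treatment-emergent window is 56 + 140 = 196 days, IV or SC.

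- With the Sub-Study 2 denominator the subject contributes 196 days, whichever tail is used for duration.
- With the Section 6.0 duration as denominator, IV and SC completers both contribute 84 days.
- With the 28/56-day duration as denominator, IV contributes 84 and SC 112. Equal event counts over equal windows would then give an SC rate 84/112 = 0.75 of the IV rate.

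**The case against.** The best defence of the common tail is that 56 + 28 = 84 days is exactly the 12-week blinded period, so all arms with planned dosing are treated alike. The Period 2 safety set is also exploratory (Sub-Study 1 SAP, Sections 4.0 and 9.1). Section 9.2.1 bases adverse event analyses on patient counts with Fisher's exact test, neither of which uses exposure. Neither SAP plans a comparison of Period 2 rates between sub-studies.

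The points on consequence stand. The defence of the tail stands only in part. Sub-Study 2 has the same 12-week double-dummy period and still splits by route, and the convention does not fit an SC subject with a single dose, who is placed in the 1–28 day band on an 8-week regimen.

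A reader might go further and infer that Sub-Study 1 SC adverse event rates are overstated: by 112/84 − 1 = 33% for a two-dose subject who does not enter M16-066, and twofold (56/28) for a one-dose subject. The documents do not establish this. Section 6.0 is the only exposure that the Sub-Study 1 SAP defines, so the link is natural, but Section 9.2.4 does not make it. Nor are SC rates shown to be inflated relative to IV: completers in both groups get 84 days against the same window. Nor does the tail explain a gap from Sub-Study 2 rates, which rest on the 140-day denominator.

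**Conclusion.** The inconsistency holds for the exposure summary. By the sponsor's own Sub-Study 2 rule, Sub-Study 1 Period 2 SC duration is short by 28 days for subjects who do not enter M16-066. The shortfall is nil for entry at Week 24 and 7 days for entry a week later. The arm-level size depends on an unreported roll-over share; between 30% and 70%, the SC completer mean is 84 days against 103.6 to 92.4. The one-dose figure assumes that dummy infusions are not counted.

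An effect on adverse event rates is unproven, because the denominator is undefined. This is a minor point in an exploratory, descriptive analysis.

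**What to change.** In the Sub-Study 1 SAP, or as a documented note in the clinical study report:

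1. **Exposure table.** Use the Sub-Study 2 tail for Period 2 (28 days after IV, 56 after SC), capped at the first M16-066 dose. Define the dose date by active doses, infusion or injection, and exclude dummy doses. Rerun the table.
2. **Adverse event rates.** State the Section 9.2.4 denominator. Do not use the 28/56-day duration, which would set 84 IV days and 112 SC days against the same 196-day window. Use last minus first dose plus 140 days, as in Sub-Study 2 SAP Section 10.2, ended at the first M16-066 dose. That formula as written has no such end point: a subject entering on day 84 would contribute 196 days against an 84-day window. Use one dose-date definition for both denominator and window.

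The cost is one changed derivation line for exposure, one sentence defining the rate denominator, and reruns of descriptive tables. No new data are needed.
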